STRIDE SAP

STRATEGIES TO REDUCE INJURIES AND DEVELOP CONFIDENCE IN ELDERS (STRIDE)

RANDOMIZED TRIAL OF A MULTIFACTORIAL FALL INJURY PREVENTION STRATEGY

STATISTICAL ANALYSIS PLAN

Version 2.0

November 25, 2019

The SAP was prepared by the blinded trial statisticians:

[name]

[name]

[name]

[name]

Revisions to the SAP were done before unblinding of the data.

STRIDE SAP

Modification to the SAP on 2-10-2020 for the Analysis of the Secondary Outcome All Falls

For the secondary outcome, all falls, the dates of events were not recorded. Thus, the analytic plan for first fall was modified from a time-to-event analysis to a practice-level Poisson model using time from baseline to the midpoint of the interview window in which the first fall was recorded as an offset in the model. [Note, the practice-level model was the default model when issues were encountered with patient-level models.] The lack of actual event times also precluded the calculation of cumulative incidence rates, which were replaced by event rates per person year of follow up. The analysis of recurrent falls was analyzed using the same method as the other recurrent event outcomes, i.e., a practice-level Poisson model with an offset for total follow-up time.

Modification to the SAP on 8-1-2020 for the Analysis of the Secondary Outcome All Falls

For the secondary outcome, all falls, the dates of events were not recorded and the exact counts of the number of events were also not recorded. Thus, a proper analysis of time to first fall and recurrent falls could not be done.

STRIDE SAP

TABLE OF CONTENTS

STUDY SUMMARY

PROTOCOL VERSION HISTORY

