6.3 Power for Secondary Outcomes

Power for all fall injuries and all falls (regardless of injury) was calculated using the same assumptions as above, but with a 1% Type I error to control for multiplicity and no adjustment for interim analysis. Annual rates of first fall and first fall injury from MOBILIZE Boston are 0.92 (95%CI: 0.75, 1.10) and 0.57 (95%CI: 0.46, 0.69), respectively. Using conservative rates of 0.70 and 0.40, and based on the targeted sample size of 6000, power is > 99% to detect a 20% reduction with intervention relative to control for both of these secondary outcomes. For the indicators of well-being, an unadjusted sample size of 524 participants is required to detect a standardized effect size of 0.3 between intervention and control at 1 and 2 years with 80% power and 1% type I error. The sample size adjusted for missing outcomes due to death (10%/year) and lost to follow-up (5%/year with or without a serious fall injury), and for clustering (DE = 6% assuming ICC = 0.0076 with 86 practices each enrolling 8 participants) is 720 (360 per group), a 12% subsample of the 6000 participants to be accrued during year 1 of the trial.

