8 ANALYTIC PLAN

8.1 Overview

The analysis of the primary and secondary outcomes will be according to the principle of intent-to-treat, i.e., practices/participants will be analyzed according to their original treatment assignment regardless of adherence to protocol. All analyses will account for the cluster design with the participant as the unit of analysis. SAS 9.4 and R 3.6.1 software will be used for all analyses.

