Cumulative incidence rates: The cumulative incidence of first serious fall injury will be estimated using non-parametric maximum likelihood methods (Aalen-Johansen estimator; Putter et al, 2006) and will be used to estimate freedom from falling over the entire follow-up period.

Supplementary Practice-level analysis: This analysis will be based on a Poisson regression model using total practice-level follow-up time as an offset, adjusted for healthcare system and the cluster-level covariates [healthcare system; constrained-covariate randomization balancing factors: practice size (tertiles), geography (urban vs. rural), and race/ethnicity (primary identification: nonwhite vs. white)]. [We note that the practice-level analysis is a planned supplementary analysis and will default to the primary analysis only if the multistate and Zhou models do not converge.]

STRIDE SAP

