8.3.2 Supportive Analysis of the Primary Outcome: Adjudicated Confirmed Recurrent Events

Analysis	Supportive analysis of primary outcome: all adjudicated confirmed serious fall injuries (recurrent events)
Analysis population	All enrolled participants
Endpoint	Times to recurrent adjudicated confirmed serious fall injuries
Unit of analysis	Participant
Method of analysis*	Joint frailty model with recurrent events and death as a semi-competing risk (Jung et al., 2018).
Calculation of follow-up time	Time from date of enrollment to the earlier of date of the last completed patient or proxy interview, or date of death.
Adjustment covariates	Cluster-level covariates: healthcare system; constrained-covariate randomization cluster-level balancing factors: practice size (tertiles), geography (urban vs. rural), and race/ethnicity (majority primary identification: nonwhite vs. white)
Type I error	5% (2-sided)
Control of type I error	None
Treatment effect estimate	Hazard ratio with 95% confidence limits

*If the Jung model does not converge, we will fit a practice-level analysis as described above.

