8.4 Analysis of Secondary Outcomes

The secondary outcomes are self-reported fall injuries, self-reported falls and indicators of well-being (fall efficacy, physical function, anxiety and depressive symptoms). Also included as a secondary outcome is unadjudicated patient-reported serious fall injuries under the original definition. To provide some control for multiplicity, we will test the secondary outcomes using a significance level of 1% (2-sided) and report 99% confidence limits.

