8.4.1 All Fall Injuries and All Falls

These endpoints will be based on patient-reported events and analyzed as both time to first event and recurrent events using the methodology outlined for the primary outcome. Patient-reported serious fall injuries under the original definition will be analyzed similarly.

STRIDE SAP

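### The practice-level Poisson model in SAP 8.3.1 names no allowance for between-practice variation; fitted as plain Poisson, its nominal 5% test runs at about 11% at the planning design effect

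*SAP*

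**What the plan says.** Section 8.3.1 describes the supplementary practice-level analysis as "a Poisson regression model using total practice-level follow-up time as an offset, adjusted for healthcare system and the cluster-level covariates". The covariates are healthcare system, practice size in tertiles, geography and race/ethnicity. Nothing is said about how the variance is estimated.

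The general rule in 8.1 is: "All analyses will account for the cluster design with the participant as the unit of analysis". No method is attached to it.

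The same model is used or referred to in several places:

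- **8.3.1, first serious fall injury.** It is a planned supplementary analysis and "will default to the primary analysis only if the multistate and Zhou models do not converge".
- **8.3.2, recurrent serious fall injuries.** "If the Jung model does not converge, we will fit a practice-level analysis as described above".
- **8.4.1, secondary fall outcomes.** These are "analyzed as both time to first event and recurrent events using the methodology outlined for the primary outcome", so the fallback carries over. Under 8.4, "we will test the secondary outcomes using a significance level of 1% (2-sided) and report 99% confidence limits".
- **Modification note of 2-10-2020.** It records that "the practice-level model was the default model when issues were encountered with patient-level models" and describes a practice-level Poisson model with a follow-up offset as the method for the other recurrent-event outcomes. It gives no variance method either.

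All falls is outside this point, because the note of 8-1-2020 says that outcome could not be properly analysed. By contrast, the Poisson model for hospitalizations in 8.5 does say that practice-level clustering will be accounted for.

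**The concern.** One count per practice can look as though clustering has been dealt with. It has not. A Poisson model sets the variance of each practice's count equal to its mean, so any difference between practices beyond the fixed covariates is left out of the standard error. The treatment is assigned by practice, so that omitted variation is what the treatment comparison should be judged against. Intervals come out too narrow and the test rejects too often.

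The SAP treats this variation as material. Appendix B, 2a inflates the event target for it, and 7.3 sets up monitoring of a variance inflation factor after the DSMB raised inter-practice variation. A fallback test that ignores it is not the test the trial was sized for.

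At stake are the supplementary first-event analysis, the primary result if both patient-level models fail, the recurrent-event analysis in 8.3.2, and two secondary outcomes tested at 1%: all fall injuries, and patient-reported serious fall injuries under the original definition.

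**Working it through.** **Inputs from the SAP.** Mean of 70 participants per practice, 86 practices, ICC 0.0076 (6.2; Appendix B, 2a); 844 events before clustering and an interim inflation of 1.03 (Appendix B, 2a); control rate 0.14 per year, deaths 7% and losses 3% per year (6.2); two-sided levels of 5% (8.3) and 1% (8.4).

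**Step 1: reproduce the plan's figures.**

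- Events: 4(1.960 + 1.282)² / (ln 0.80)² = 844.1, agreeing with 844.
- Design effect: DE = 1 + (70 − 1) × 0.0076 = 1.524, agreeing with 1.52.
- Target: 844 × 1.52 × 1.03 = 1321, as stated.

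**Step 2: level of a test that ignores clustering.** If the true variance of the log rate ratio is DE times the Poisson variance, then

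actual type I error = 2 × [1 − Φ(z / √DE)].

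With √1.524 = 1.235:

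- Nominal 5%: 1.960 / 1.235 = 1.587, giving 11.2% (coverage 88.8%).
- Nominal 1%: 2.576 / 1.235 = 2.086, giving 3.7% (coverage 96.3%).

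The 1% figure applies to all fall injuries because 6.3 says its power "was calculated using the same assumptions as above, but with a 1% Type I error to control for multiplicity".

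**Step 3: range.** The SAP gives no design effect remaining after adjustment, so the absorbed shares and the practice-size coefficient of variation (CV) are assumptions. For a CV of 0.5, DE = 1 + (1.25 × 70 − 1) × 0.0076 = 1.657.

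| Assumed case | DE | Nominal 5% | Nominal 1% |
|---|---|---|---|
| Nothing absorbed, practice-size CV 0.5 | 1.657 | 12.8% | 4.5% |
| Nothing absorbed, equal sizes | 1.524 | 11.2% | 3.7% |
| 50% of excess absorbed | 1.262 | 8.1% | 2.2% |
| 80% absorbed | 1.105 | 6.2% | 1.4% |
| 90% absorbed | 1.052 | 5.6% | 1.2% |
| All absorbed | 1.000 | 5.0% | 1.0% |

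At the enrolled mean of 5,451 / 86 = 63.4 per practice, DE is 1.474 and the error is 10.6% with nothing absorbed and equal sizes.

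**Step 4: simulation under no treatment effect.** 86 practices in 10 systems, control rate 0.14, death and loss combined 0.10 per year, 15 parameters (intercept, treatment, 9 for system, 2 for size, 1 each for geography and race/ethnicity), hence 71 residual df; 4,000 trials per case. The Monte Carlo standard error is about 0.34 points at a true 5% and 0.16 points at a true 1%. Entries are rejection rates at nominal 5% / 1%.

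| Case | Plain Poisson | Quasi-Poisson, t | Negative binomial, t |
|---|---|---|---|
| Nothing absorbed | 11.2 / 3.6% | 4.9 / 0.6% | 4.8 / 0.6% |
| 50% absorbed | 8.0 / 2.0% | 4.4 / 0.9% | 4.4 / 0.9% |
| 80% absorbed | 6.3 / 1.2% | 4.7 / 0.8% | 4.6 / 0.8% |
| All absorbed | 4.9 / 1.1% | 3.8 / 0.7% | 3.9 / 0.7% |
| Nothing absorbed, CV 0.5 | 12.6 / 4.7% | 5.9 / 1.5% | 5.3 / 1.4% |

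The simulation agrees with the closed form.

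**Step 5: recurrent events, illustration only.** Repeat injuries in one person add further extra-Poisson variation, and the SAP gives nothing from which to size it. With an assumed patient frailty variance of 0.65, plain Poisson rejects 7.5% / 1.6% with no practice variation and 14.4% / 5.5% with the planning practice variation. Quasi-Poisson with t gives 4.8% / 0.7% and 5.0% / 1.2%.

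**The case against.** The strongest reply is that silence is not contradiction. Section 8.1 covers every analysis, and nothing in 8.3.1 says that clustering is ignored, so only an analyst who disregards 8.1 reaches plain Poisson. This stands in part: 8.1 shows the intent. But it names no method and ties its promise to the participant as unit, which this model is not. The Poisson model in 8.5 restates clustering; the one that can become primary does not.

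Second, 11% is not an established error rate for this trial. That is correct. It requires plain Poisson and the whole planning design effect left after adjustment, and Appendix B, 2a itself says the design effect must be re-estimated. The figure is conditional and belongs with its range.

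Third, the primary fallback may be remote. Table A of Appendix B projects 11,589 person-years, or about 135 per practice (11,589 / 86). At 0.10 to 0.14 per year that is roughly 13 to 19 events in an average practice, so zero-event practices, which the 8.3.1 footnote cites as a cause of convergence trouble, would arise mainly among small ones. This limits the effect on the primary result. It does not help the recurrent-event outcomes, where the 2-10-2020 note places the model.

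Fourth, at unequal practice sizes the simulated quasi-Poisson level was 5.9% / 1.5%, and 1.5% is about three standard errors above nominal. Separate runs at the same CV gave 5.7–5.9% / 1.0–1.2% for quasi-Poisson and 4.9–5.1% / 0.9% for negative binomial. The remedy holds the level approximately, and negative binomial does slightly better.

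Fifth, the SAP is dated November 2019 and the study was due to end in April 2020, so new text may no longer be prospective. That is fair, and the fix therefore includes a reporting request.

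**Conclusion.** The point holds and should be fixed. As written, 8.3.1 does not deliver what 8.1 promises, and an analyst who follows it literally obtains standard errors that are too small whenever practices differ beyond the covariates.

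For first events the size is 11.2% at nominal 5% and 3.7% at nominal 1%, assuming plain Poisson, DE 1.524 and nothing absorbed by the covariates. Over the assumed cases it runs from nominal to 12.8% / 4.5%. For recurrent events the direction is clear, but the SAP does not allow the size to be fixed.

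The primary result is touched only if both the multistate and Zhou models fail. Nothing in the SAP shows that plain Poisson was actually used.

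**What to change.** Add to 8.3.1, and carry to 8.3.2 and 8.4.1: *The practice-level model will allow for extra-Poisson variation between practices, by quasi-Poisson with Pearson dispersion floored at 1 or by negative binomial, the choice being named before the fit, with a t reference on residual degrees of freedom.* Either is acceptable; negative binomial has a slight advantage when practice sizes vary widely.

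For any practice-level analysis already run, state which variance was used, and recompute its intervals only if it was plain Poisson.

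The cost is one sentence and possibly a re-run. Intervals widen by about the square root of the dispersion: 23% at 1.52, 12% at 1.26 and 5% at 1.10. The t reference on 71 df adds about 1.7% to 95% limits and 2.8% to 99% limits. For first events the widening at 1.52 is already paid for in the target of 1321. If no extra variation remains, the floor makes the test slightly conservative (3.8% simulated at nominal 5%).

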8.3.2 Supportive Analysis of the Primary Outcome: Adjudicated Confirmed Recurrent Events

Analysis	Supportive analysis of primary outcome: all adjudicated confirmed serious fall injuries (recurrent events)
Analysis population	All enrolled participants
Endpoint	Times to recurrent adjudicated confirmed serious fall injuries
Unit of analysis	Participant
Method of analysis*	Joint frailty model with recurrent events and death as a semi-competing risk (Jung et al., 2018).
Calculation of follow-up time	Time from date of enrollment to the earlier of date of the last completed patient or proxy interview, or date of death.
Adjustment covariates	Cluster-level covariates: healthcare system; constrained-covariate randomization cluster-level balancing factors: practice size (tertiles), geography (urban vs. rural), and race/ethnicity (majority primary identification: nonwhite vs. white)
Type I error	5% (2-sided)
Control of type I error	None
Treatment effect estimate	Hazard ratio with 95% confidence limits

*If the Jung model does not converge, we will fit a practice-level analysis as described above.

8.4 Analysis of Secondary Outcomes

The secondary outcomes are self-reported fall injuries, self-reported falls and indicators of well-being (fall efficacy, physical function, anxiety and depressive symptoms). Also included as a secondary outcome is unadjudicated patient-reported serious fall injuries under the original definition. To provide some control for multiplicity, we will test the secondary outcomes using a significance level of 1% (2-sided) and report 99% confidence limits.

8.4.1 All Fall Injuries and All Falls

These endpoints will be based on patient-reported events and analyzed as both time to first event and recurrent events using the methodology outlined for the primary outcome. Patient-reported serious fall injuries under the original definition will be analyzed similarly.

STRIDE SAP

8.4.2 Indicators of Well-Being

Indicators of well-being include fall efficacy (measured by FES), physical function (measured by LL-FDI), anxiety and depressive symptoms (measured by Promise scales for anxiety and depression) and were measured at 12 and 24 months in a random subsample of 714 participants. Each outcome will be analyzed separately as described below.

Analysis	Indicators of well-being
Analysis population	Random subsample of 714 participants
Endpoint	Scale values at 12 and 24 months of follow-up
Unit of analysis	Participant
Method of analysis	Linear mixed model assuming missing at random (MAR)
Handling of missing data	MAR assumption
Adjustment covariates	Baseline indicator of well-being; Factors predictive of missingness: these will be determined at the time of analysis
Type I error	1% (2-sided)
Treatment effect estimate	Marginal least square mean (LSM) with 99% confidence limits if there is no treatment by time interaction ($p < 0.10$); otherwise, LSM will be summarized for each treatment and timepoint

Sensitivity analyses will be conducted to investigate the MAR assumption, such as methods that model jointly the missingness and outcome distributions (National Research Council, 2010).

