8.3 Analysis of Primary Outcome: Adjudicated Serious Fall Injury

8.3.1 Primary Analysis of Primary Outcome: Adjudicated Confirmed First Event

Analysis	Primary analysis of primary outcome: adjudicated confirmed first serious fall injury
Analysis population	All enrolled participants
Endpoint	Time to first adjudicated confirmed serious fall injury
Unit of analysis	Participant
Method of analysis*	Multistate survival model that incorporates competing risks due to death and clustering (Putter et al., 2007; Lee et al., 1992; R

STRIDE SAP

	Package 'survival': https://cran.r-project.org/web/packages/survival/survival.pdf)
Calculation of follow-up time	Time from date of enrollment to the earliest of: date of first confirmed serious fall injury, date of last completed patient or proxy interview, or date of death.
Adjustment covariates	Cluster-level covariates: healthcare system; constrained-covariate randomization balancing factors: practice size (tertiles), geography (urban vs. rural), and race/ethnicity (majority primary identification: nonwhite vs. white)
Type I error	5% (2-sided)
Control of type I error	None
Treatment effect estimate	Hazard ratio with 95% confidence limits

* If the multistate model does not converge, we will fit the Zhou et al. (2011) model. In the event there are practices with no events that create convergence issues with fitting patient-level models for the primary outcome [i.e., multistate and Zhou et al. (2011)], the primary analysis will default to a practice-level analysis as described below.

Sensitivity analysis: Adjustment for pre-specified set of patient-level covariates (in addition to cluster-level covariates): age, sex, race/ethnicity, education, number of chronic conditions, and number of positive screening items for serious fall injuries.

Subgroup analysis: The effect of intervention will be evaluated in the following prespecified subgroups of participants using appropriate tests of homogeneity (e.g., interaction): age (70-79, 80+), sex (male, female), fear of falling alone (yes, no), multimorbidity (0-1 chronic conditions, 2+ chronic conditions), and hip fracture or other fracture since age 50 (yes/no)]. The Hochberg (1988) procedure will be used to control for multiplicity for the tests of interaction using an overall type I error of 5% (2-sided).

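### The well-being analysis uses a 0.10 interaction test to choose its estimand, and names no contrast for the 1% test once interaction is declared

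*SAP*

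**What the plan says.** Section 8.4 covers every secondary outcome: "we will test the secondary outcomes using a significance level of 1% (2-sided) and report 99% confidence limits". It presents this as giving some, not full, control of multiplicity.

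Section 8.4.2 analyses each well-being indicator with a linear mixed model. The endpoint is "Scale values at 12 and 24 months of follow-up", with no lead visit, and the Type I error row repeats 1% two-sided. The treatment effect row has two branches. The first is "Marginal least square mean (LSM) with 99% confidence limits if there is no treatment by time interaction", followed by a threshold of 0.10. The second is "otherwise, LSM will be summarized for each treatment and timepoint".

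Section 6.3 sizes the subsample for a "standardized effect size of 0.3 between intervention and control at 1 and 2 years with 80% power and 1% type I error".

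The covariate row in 8.4.2 reads "Baseline indicator of well-being; Factors predictive of missingness: these will be determined at the time of analysis". The models in 8.3.1 and 8.3.2 also carry healthcare system, practice size tertile, geography and race/ethnicity, the factors that 5.1 used for stratified, covariate-constrained randomisation.

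**The concern.** A test result decides what is estimated. In one branch that is an effect averaged over the visits. In the other it is a set of arm-by-visit means, and a mean in one arm is not a treatment effect. The 1% test and the 99% limits promised in 8.4 therefore have no named difference to attach to, and nothing says whether 1% covers one visit, each visit, or both together.

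Two things are at stake for each of the four indicators: whether it is tested at all when the effect changes over time, and what error rate its test has. A fall-prevention effect that builds up or fades is plausible, so the second branch is not a remote case.

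As printed, the 0.10 threshold also follows the condition of no interaction, which reverses the evident meaning. The working below takes p < 0.10 as the criterion for declaring interaction.

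**Working it through.** **The plan's own figure.** Inputs from 6.3: effect 0.3 SD, 80% power, two-sided 1%. A two-sample t test needs 261.2 per arm, so 262 per arm or 524 in total, matching "an unadjusted sample size of 524 participants is required to detect a standardized effect size of 0.3". With 524, power is 80.1% at 1% and about 73% at 0.5%. So 524 is the size for one visit at the full 1%, with no split over two visits.

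**Set-up.** Each visit's estimated difference is taken as normal with equal variance and 80% power for 0.3 SD at 1%. This gives θ = 0.3/SE = 2.576 + 0.842 = 3.417. Let ρ be the correlation between the 12- and 24-month estimates. It is not in the SAP, so a range is assumed. Let w₁ and w₂ be the true effects divided by 0.3.

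- Average contrast: mean z = θ(w₁ + w₂)/√(2(1 + ρ)), critical value 2.576.
- Interaction contrast: mean z = θ(w₂ − w₁)/√(2(1 − ρ)), critical value 1.645.

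With equal variances these two contrasts are independent.

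**Second branch read as descriptive.** A positive result needs a significant average and no declared interaction, so the two probabilities multiply.

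- No effect: 0.01 × 0.90 = 0.9%.
- Effects 0.15 and 0.30 SD (w = 0.5 and 1), ρ = 0.5: average z = 3.417 × 1.5/√3 = 2.96, power 65%. Interaction z = 3.417 × 0.5/√1 = 1.71, declared in 53% of trials. Power = 0.650 × 0.474 = 31%.
- ρ = 0.3: 0.727 × 0.579 = 42%. ρ = 0.7: 0.581 × 0.287 = 17%.

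**Second branch read as a difference at each visit at 1%.** This was simulated (4 million null draws, 1 million per alternative).

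| | ρ = 0.3 | 0.5 | 0.7 | 0.9 |
|---|---|---|---|---|
| Null: interaction declared | 10.0% | 10.0% | 10.0% | 10.0% |
| Null: error if descriptive | 0.89% | 0.90% | 0.91% | 0.89% |
| Null: error, each visit at 1% | 1.95% | 1.73% | 1.48% | 1.20% |
| Null: error, 0.5% per visit after the pre-test | 1.49% | 1.36% | 1.22% | 1.06% |
| 0.15 and 0.30 SD: interaction declared | 42% | 53% | 71% | – |
| 0.15 and 0.30 SD: power, each visit at 1% | 82.0% | 78.6% | 77.8% | – |
| Constant 0.30 SD: power if descriptive | 85.7% | 82.3% | 78.4% | – |
| Constant 0.30 SD: power, each visit at 1% | 95.6% | 92.2% | 88.1% | – |

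Splitting the 1% only after interaction is declared does not bring the error back to 1%, because the average has already had its own chance at the full 1%.

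**Rules fixed without a pre-test** (power in %, ρ = 0.3/0.5/0.7; null error over ρ = 0.3 to 0.9).

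| Rule | Null error | Constant 0.30 SD | 0.15 and 0.30 SD | 0.30 SD at one visit only |
|---|---|---|---|---|
| Average of both visits | 1.0% | 95/92/87 | 73/65/58 | 32/27/24 |
| One named visit | 1.0% | 80 | 80, or 19 if that visit has 0.15 | 80, or 1 if that visit has no effect |
| 0.5% per visit | 0.98% to 0.76% | 89/86/83 | 75/74/73 | 73 |
| Hochberg over the visits | 0.99% to 0.84% | 90/87/84 | 75/74/73 | 73 |

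Testing each visit at 1% with no pre-test gives a per-outcome error of 2.0%, 1.9% and 1.8% at ρ = 0.3, 0.5 and 0.7.

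**Randomisation factors.** With the ICC of 0.0076 and 8 per practice in 6.3, the design effect is 1 + 7 × 0.0076 = 1.053. On the normal approximation, 524 gives z = 0.3 × √(524/4) = 3.434 and power 80.5%. Removing all between-practice variance gives z = 3.434 × √1.053 = 3.524 and power 82.8%. The gain is therefore at most 2.3 points. Simulation with half to all of that ICC lying between systems (an assumption) gives a loss of about 0 to 2 points from omission, with type I error of 0.6% to 1.0%.

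**The case against.** The plan is less open than 8.4.2 alone suggests. A reader might infer four stronger criticisms, and the SAP does not support them.

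- *No confidence limits are set for the second branch.* Section 8.4 sets 99% limits for every secondary outcome. Only the contrast they belong to is missing.
- *Someone must pick the deciding visit after seeing the results.* Section 6.3 plans for an effect at 1 and 2 years at 1%, and 8.4 says to test at 1%. Together they favour a difference at each visit, both reported, so no visit need be picked.
- *The plan breaks a firm guarantee of 1% per outcome.* Section 8.4 claims only partial control, and 8.4.1 analyses each fall outcome both as first event and as recurrent events without splitting the 1%. One per cent per analysis is a fair reading of the plan's habit.
- *Leaving out the randomisation factors invalidates the test.* Section 8.1 already requires clustering to be handled, and the omission makes the test slightly conservative.

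The excess error is also small, and its upper end needs a low assumed correlation. Every alternative rule gives up power in some pattern of effects, so choosing among them is a trade-off.

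What stands is narrower. The SAP does not write down the by-visit reading. The descriptive reading is the literal one. The error rate differs between the two.

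**Conclusion.** The point holds as a gap in specification with a modest effect on error. The 0.10 pre-test chooses the estimand, and the second branch does not name the between-group difference to be tested or say how 1% applies to two visits.

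Under the literal, descriptive reading, the outcome goes untested in the trials where the visits are found to differ, and power for 0.15 and 0.30 SD is about 17% to 42%. Under the more natural by-visit reading, power is about 78% to 82%, and the error per outcome is about 1.2% to 2.0% instead of 1%.

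These figures rest on equal variances at the two visits, 80% power per visit, and assumed correlations of 0.3 to 0.7 for power and 0.3 to 0.9 for error. They also take p < 0.10 as declaring interaction. The matter is worth settling but concerns secondary outcomes only.

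The covariate omission is minor at the plan's ICC. That ICC comes from serious fall injuries (6.2), so its fit to well-being scales is unknown.

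**What to change.** 1. State one confirmatory 1% rule for each well-being indicator that applies whatever the interaction test shows. The sponsor chooses among the average of 12 and 24 months, one named visit, or both visits sharing the 1%. Sharing can be 0.5% each or by the procedure the SAP already adopts for subgroups ("The Hochberg (1988) procedure will be used to control for multiplicity for the tests of interaction"). The power cost of the chosen rule, as in the second table, should be stated beside it. Keeping 80% power per visit at 0.5% would need 298 per arm, about 596 in total before adjustment, against 524.
2. If the sponsor prefers each visit at the full 1%, say that the 1% is per visit and that the error per outcome is up to about 2%.
3. Always report the between-group difference at each visit with 99% limits, and give the interaction as description.
4. Correct the wording so that the 0.10 threshold no longer sits on the condition of no interaction.
5. Add healthcare system, practice size tertile, geography and race/ethnicity to the 8.4.2 model, as in 8.3.1 and 8.3.2. With 10 systems this uses 9 + 2 + 1 + 1 = 13 degrees of freedom.

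All of this is a few sentences in the SAP and variables already held. No new data are needed.
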